#### 9.2.5. Documenting and Reporting Serious Pretreatment Events and Serious Adverse Events

All SAEs that occur after obtaining informed consent through the EOS Visit, regardless of causality, must be reported by the Investigator or designee to

and Enanta Pharmaceuticals, Inc. In addition, all SAEs, including those that result in death, that occur after the EOS Visit and that are considered related to study drug must be reported to and Enanta Pharmaceuticals, Inc. within 24 hours of learning of its occurrence. Additional details are provided in the Safety Management Plan.

The SAE Form should be sent to

via email at

All SAEs will be recorded on the SAE Form using a recognized medical term or diagnosis that accurately reflects the event. All SAEs will be assessed by the Investigator for severity, relationship to the investigational study drug, and possible etiologies. On the SAE Form, relationship to study drug will be assessed only as related or not related. For the purposes of study analysis, if the event has not resolved at the end of the study reporting period, it will be documented as ongoing. For purposes of regulatory safety monitoring, the Investigator is required to follow-up the event to resolution and report the outcome of the event to mand Enanta Pharmaceuticals, Inc. using the SAE Form.

The Investigator or designee is responsible for notifying the Sponsor within 24 hours of identifying an SAE, regardless of the presumed relationship to the investigational study drug. The SAE Form should be completed for new/initial events as well as to report follow-up information on previously reported events. The Investigator or designee is asked to report follow-up information as it becomes available.

Enanta Pharmaceuticals, Inc. or its designees, as study Sponsor, is responsible for reporting suspected, unexpected, serious adverse reactions (SUSAR) involving the study drug to all regulatory authorities, and participating investigators, in accordance with US Food and Drug Administration (FDA), International Council for Harmonisation (ICH) guidelines, and/or local regulatory requirements, as applicable.

# 9.3. Follow-up of Adverse Events and Serious Adverse Events

All AEs (serious and nonserious) will be followed up until resolution or otherwise explained (see Table 5), the subject dies, the event stabilizes and is not expected to further resolve with the maximum time limit for stabilization defined as 30 days after the occurrence of the event, or when alternative therapy is instituted, whichever occurs first. If alternative therapy is instituted, it should be documented. Enanta Pharmaceuticals, Inc. may request that the Investigator perform or arrange for supplemental measurements or evaluations to further clarify the nature of the event.

# 9.4. Sponsor's Review of Adverse Events and Serious Adverse Events

Enanta Pharmaceuticals, Inc. will maintain an ongoing review of all AEs and SAEs.

## 10. SUBJECT SAFETY MANAGEMENT/STUDY STOPPING RULES

## **10.1.** Study Stopping Rules

If any of the following events occur, dosing will be placed on hold pending a full review of all available clinical safety data and discussion with the investigators and the SSC.

- Two or more subjects receiving study drug experience a similar Grade 3 study drug-related AE, including a confirmed treatment-emergent Grade 3 laboratory abnormality;
- One or more subjects receiving study drug experience a study drug-related SAE;
- One or more subjects receiving study drug experience Grade 4 or higher AE or a confirmed treatment-emergent laboratory abnormality regardless of causality attribution to study drug.

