## 4.2. Study Monitoring Committees

## 4.2.1. Study Steering Committee

An SSC blinded to treatment assignment will ensure the continuing safety of subjects enrolled to the study through scheduled and as needed evaluations of data to inform dose selections and to review events that meet stopping rule criteria. The SSC will have access to available blinded data, including at least safety and PK data. As described in Section 4.1, the SSC will review data from each cohort and will determine dose selection and cohort progression in Part 1 and Part 2. The SSC will include the Enanta Medical Monitor, an Enanta clinical pharmacology

representative, a biostatistician, a pediatrician with expertise in respiratory infections and who is independent of the study conduct, and the Contract Research Organization's Medical Monitor.

The SSC will not allow progression to the next cohort/part if there are two or more of the same study drug-related Grade 3 adverse events, one or more study drug-related Grade 4 adverse events, or one or more study drug-related serious adverse events. In order to proceed to the next cohort under these circumstances, the IDMC would be required to review the relevant data and agree with proceeding.

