# 8.11. Laboratory and Diagnostic Procedures

Blood samples will be collected for analysis of the analytes as shown in Table 3. Samples will be collected from all subjects enrolled into the study.

The maximum blood volume collected at a single collection is approximately and the maximum total blood volume collected in study for each subject is approximately **block**. Maximum blood draw volumes will be adjusted to be within accepted minimal risk guidelines as per local standard of care.

Procedures performed as part of standard of care up to 72 hours before informed consent may be used in determining study eligibility and to determine baseline values.

For subjects who have screening and randomization separated by more than 24 hours, blood sampling for clinical laboratory tests should be done predose on Day 1 for baseline values. This blood sampling does not need to be done for subjects who have randomization within 24 hours after screening because the screening clinical laboratory test results will be used as the baseline values.

All unblinded laboratory values will be reviewed by the Investigator, documented, and the results will be maintained in the source documents. All out-of-range laboratory findings require an interpretation as to whether they are of clinical significance. Clinically significant laboratory findings in the opinion of the Investigator should be recorded as an AE (or SAE as appropriate) (see Section 9.1).

Blood and urine samples for clinical laboratory assessments will be collected according to the SoA (Appendix 1) and all clinical laboratory assessments will be performed at the local site laboratory. Clinical laboratory tests include biochemistry, hematology, and cardiac biomarkers. Cardiac biomarkers will be tested as maximum blood draw volumes allow according to local guidelines. All subjects with new abnormal cardiac laboratory values after receiving study drug

should have echocardiograms. Urinalysis will only be conducted in subjects who are either toilet trained and able to provide a specimen or are already catheterized or fitted with a urine collection bag.

The subject's estimated creatinine clearance will be calculated using the subject's serum creatinine ( $Cr_{serum}$ ) value, height, and the appropriate equation (Schwartz & Work, 2009):

Glomerular filtration rate (mL/min per 1.73 m^2) =  $0.413 * \text{height/Cr}_{\text{serum}}$ 

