# 9.2. Documenting and Reporting of Adverse Events (Including Serious Adverse Events)

AEs will be evaluated and documented using the grading scales contained in the National Cancer Institute Common Terminology Criteria for Adverse Events (NCI-CTCAE) Version 5.0.

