#### 9.2.1. Documenting and Reporting Adverse Events

All AEs reported from the time of informed consent to the EOS Visit for each subject will be recorded in the subject's source documents. For subjects who do not receive study drug (i.e., screen failures), AEs will only be recorded in the source documents. For subjects enrolled into the study (i.e., randomized), all AEs will be recorded in the subject's AE eCRF and the SAE Form (if applicable). The site should record all AEs regardless of the intensity, seriousness, or relationship to study drug.

AEs (serious and nonserious) will be graded in accordance with the NCI-CTCAE scale as follows:

- **Mild** (Grade 1): asymptomatic or mild symptoms; clinical or diagnostic observations only; intervention not indicated;
- **Moderate** (Grade 2): minimal, local, or noninvasive intervention indicated; limiting age-appropriate instrumental activities of daily living;
- Severe (Grade 3): severe or medically significant but not immediately lifethreatening; hospitalization or prolongation of hospitalization indicated; disabling; limiting self-care activities of daily living;
- Life-threatening (Grade 4): life-threatening consequences; urgent intervention indicated;

• **Death** (Grade 5): death related to the AE.

Any recurrence of an AE with similar causality to study drug will be reported as recurrence or exacerbation of the initial event, and not as a new event. Whenever possible, AEs will be reported as a specific diagnosis or syndrome (e.g., flu syndrome) rather than as individual signs or symptoms. If no specific diagnosis or syndrome is identified, AEs should be reported as separate and individual events.

An AE includes the following:

- Progression or exacerbation of the subject's underlying disease. Clinical sequelae that result from disease progression, such as pleural effusion or small bowel obstruction, are reportable as AEs;
- Pre-existing event that increases in frequency or intensity;
- Condition detected or diagnosed during the study period, even though it may have been present, in retrospect, before the first dose of study drug;
- Laboratory abnormalities outside of normal limits with associated clinical symptoms or suspected latent clinical symptoms in the opinion of the Investigator, including those requiring therapeutic intervention;

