## **10.2.** Individual Subject Discontinuation Criteria

If one (or more) of the following changes occur, the subject should discontinue study drug and should be followed until resolution (return to baseline) or stabilization of change (to be agreed upon with the Sponsor). The Sponsor should be informed even if the change occurs outside of the treatment period (but before the end of the study).

- A TEAE which is considered clinically significant (e.g., meeting Grades 3 [severe] or 4 [potentially life-threatening] criteria) and is attributed to study drug and/or which is thought to preclude further safe administration of study drug;
- An AE/SAE, drug reaction, or complication, whether related or not to study drug, which precludes continuation of treatment with study drug;
- The Principal Investigator's opinion that it is not in the subject's best interest to continue study participation.

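### The third dosing-hold trigger in Protocol 10.1 gives no grade for laboratory abnormalities; Grade 4 is very probably meant and should be stated

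*Protocol*

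**What the plan says.** Protocol 10.1 lists three events, any one of which puts dosing on hold until the safety data have been reviewed and discussed with the investigators and the Study Steering Committee (SSC).

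- First trigger: "Two or more subjects receiving study drug experience a similar Grade 3 study drug-related AE, including a confirmed treatment-emergent Grade 3 laboratory abnormality".
- Second trigger: one or more subjects with a drug-related SAE.
- Third trigger: one or more subjects with a "Grade 4 or higher AE or a confirmed treatment-emergent laboratory abnormality regardless of causality attribution to study drug".

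The first trigger states its grade twice, once for the AE and once for the laboratory abnormality. The third states it once, before the AE.

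The parallel rule for cohort progression, in Protocol 4.2.1, blocks progression on "two or more of the same study drug-related Grade 3 adverse events, one or more study drug-related Grade 4 adverse events", or on one or more drug-related SAEs. It has no separate laboratory criterion.

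Protocol 11.5.4 describes treatment-emergent laboratory results for reporting: any move from within limits at baseline to outside them afterwards. It sets no minimum grade.

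**The concern.** In the third trigger the laboratory abnormality has its own article and no grade. On its face, a single mild change in one child is enough once it is confirmed, whatever its cause. That sits oddly beside the first trigger, which asks for two children, Grade 3 and drug-relatedness before a laboratory finding counts.

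The rule is mandatory, so site and sponsor staff have two poor options. They can follow the text and hold dosing where nobody intended it, or follow the presumed intent and depart from a written safety rule. Different people may choose differently, and the rule would then be applied unevenly across cohorts and age groups.

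**Working it through.** The documents state no operating characteristic for the stopping rules, so there is no figure to reproduce. The check is one of logic.

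**Step 1: does another section supply the grade?**

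- Protocol 4.2.1 shows the likely ladder, but it concerns progression, names only drug-related adverse events and has no laboratory limb.
- Protocol 11.5.4 has no grade floor, so it does not narrow the third trigger.
- No other section of the protocol or SAP adds a grade to this trigger.

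**Step 2: what each wording does.** Take confirmed, treatment-emergent, non-serious laboratory abnormalities that are not themselves recorded as Grade 4 AEs.

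| Laboratory finding | Text as it stands | With Grade 4 or higher inserted |
|---|---|---|
| Grade 1 or 2, any number of children, any cause | Hold (third trigger) | No hold |
| Grade 3, one child, any cause | Hold (third) | No hold |
| Grade 3, two or more children, not drug-related | Hold (third) | No hold |
| Grade 3, two or more children, similar and drug-related | Hold (first and third) | Hold (first only) |
| Grade 4, one or more children, any cause | Hold (third) | Hold (third) |

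The fourth row is the only one where the first trigger's laboratory limb is met. Under the present text the third trigger is met there too, so that limb decides nothing. With the grade inserted, it decides that row.

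**Step 3: the same check by enumeration.** Give each of two children a laboratory grade from 0 to 4 and a related or not-related label: 5 x 5 x 2 x 2 = 100 states, with abnormalities in both children taken as similar. The first trigger's laboratory limb is met in 1 state (both Grade 3, both related).

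- States meeting that limb but not the third trigger, present text: 0.
- The same, with Grade 4 or higher inserted: 1.

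These counts show redundancy only. The states are not equally likely, and the proportions depend on how the grid is drawn.

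**Step 4: how often might it bite?** The documents give no rate of confirmed laboratory abnormalities. As an illustration only, assume that a fraction p of children have one of any grade, independently. The chance of at least one in n children is 1 - (1 - p)^n. For the 12 children planned per Part 1 cohort and age group (SAP 4.2):

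- p = 5%: 1 - 0.95^12 = 46%
- p = 10%: 1 - 0.90^12 = 72%
- p = 20%: 1 - 0.80^12 = 93%
- p = 30%: 1 - 0.70^12 = 99%

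If only the 8 children on EDP-938 count, the range is 34% (p = 5%) to 94% (p = 30%). These figures rest wholly on the assumed p.

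**The case against.** The strongest reply is that this is a drafting slip whose meaning is clear in context. The first trigger pairs a Grade 3 AE with a Grade 3 laboratory abnormality, 4.2.1 has the same two-Grade-3 or one-Grade-4 ladder, and the phrase can be read with the grade carried over to its second half. A reading that empties another limb of the same rule is itself a reason to prefer the alternative. This stands as evidence of intent, and Grade 4 is very probably what was meant. It does not remove the defect: the separate article weakens the carry-over reading, and a mandatory threshold should not have to be inferred.

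The second reply is that the consequence is limited: a hold pending review, not termination. The requirement for confirmation also screens out one-off spurious readings, though not mild ones. This stands in full and is why the point is minor.

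Three stronger readings are tempting, and the documents do not support them.

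- *Section 10 mixes two grading scales.* A reader might infer this because 10.2 speaks of "meeting Grades 3 [severe] or 4 [potentially life-threatening] criteria", close to the label that SAP 4.14.2 gives to Grade 4 under DAIDS, while 9.2.1 has "Life-threatening (Grade 4): life-threatening consequences; urgent intervention indicated". But that bullet of 10.2 concerns treatment-emergent AEs, which 9.2.1 grades by CTCAE. DAIDS appears only in the SAP, for tables and listings, and the first trigger treats a laboratory abnormality as a kind of AE. What remains is narrow. Protocol 9.2 says "AEs will be evaluated and documented using the grading scales contained in the National Cancer Institute Common Terminology Criteria for Adverse Events", and a laboratory value becomes an AE only on judgement (8.11: "Clinically significant laboratory findings in the opinion of the Investigator should be recorded as an AE"; 9.2.1: "Laboratory abnormalities outside of normal limits with associated clinical symptoms or suspected latent clinical symptoms in the opinion of the Investigator"). A value under the third trigger that is not recorded as an AE therefore has no explicitly assigned scale.
- *The whole first trigger is redundant.* Only its laboratory limb is. Two similar drug-related Grade 3 clinical AEs still hold dosing through the first trigger alone.
- *The counts in the working measure how many holds will be unintended.* They do not. They follow from the missing grade and carry no event rates.

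**Conclusion.** The concern holds as a minor wording error in a decision threshold. The laboratory limb of the third trigger has no grade, no other section supplies one, and on the literal text the first trigger's laboratory limb never decides an outcome (0 of the 100 enumerated states, against 1 once the grade is inserted).

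The error runs in the cautious direction. It can produce unintended holds, or holds applied inconsistently, but it does not let a signal through. No endpoint, analysis population or estimate is affected.

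The conclusion rests on the wording alone. It needs no assumed event rate, and the hold probabilities shown above are not part of its support. That Grade 4 was intended is an inference from the first trigger and from 4.2.1, and the sponsor should confirm it.

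**What to change.** In the third bullet of Protocol 10.1, insert *Grade 4 or higher* directly before *laboratory abnormality*, and set off the two limbs with commas so that the causality clause plainly covers both. The trigger would then cover a Grade 4 or higher AE, or a confirmed treatment-emergent Grade 4 or higher laboratory abnormality, in either case whatever its attributed cause.

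Optionally, add one sentence to 10.1 saying that laboratory grades there use CTCAE v5.0, the only scale the protocol names. This covers values that are not recorded as AEs. The SAP can go on tabulating laboratory grades by DAIDS, since that is for reporting. Readers should then expect that a grade used for a hold may differ from the grade in a table.

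The cost is one reworded bullet and, if wanted, one added sentence, carried in a protocol amendment with the usual ethics review. No SAP change, extra data or additional subjects are needed.

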## **10.2.** Individual Subject Discontinuation Criteria

If one (or more) of the following changes occur, the subject should discontinue study drug and should be followed until resolution (return to baseline) or stabilization of change (to be agreed upon with the Sponsor). The Sponsor should be informed even if the change occurs outside of the treatment period (but before the end of the study).

- A TEAE which is considered clinically significant (e.g., meeting Grades 3 [severe] or 4 [potentially life-threatening] criteria) and is attributed to study drug and/or which is thought to preclude further safe administration of study drug;
- An AE/SAE, drug reaction, or complication, whether related or not to study drug, which precludes continuation of treatment with study drug;
- The Principal Investigator's opinion that it is not in the subject's best interest to continue study participation.

## **10.3.** Cohort Discontinuation Criteria

Further enrollment within a cohort or enrollment to subsequent cohorts will be discontinued once it has been established that safety risk(s) such as the following occur:

- If any unacceptable toxicity (as determined by the Sponsor Medical Monitor) occurs;
- If the SSC considers an event or multiple events to represent an unacceptable risk to the health and well-being of subjects at that or higher dose levels.

## **10.4.** Site or Study Discontinuation

#### **10.4.1.** Study Discontinuation

The Sponsor has the right to terminate this study at any time. Reasons for terminating the study may include, but are not limited to, the following:

• The incidence or severity of AEs in this study indicates a potential health hazard to subjects;

- Subject enrollment is unsatisfactory;
- Data recording is inaccurate or incomplete;
- Investigator does not adhere to the protocol or applicable regulatory guidelines in conducting the study;
- A decision from the IRB/EC or regulatory authority to terminate the study.

If the study is suspended or terminated for safety reasons, Enanta Pharmaceuticals, Inc. will promptly notify the investigators and will also inform the regulatory authorities of the suspension or termination of the study and the reasons for the action. The Investigator is responsible for promptly informing the IRB/EC and providing the reasons for the suspension or termination of the study.

#### **10.4.2.** Site Termination

A single site may warrant termination under the following conditions:

- Failure of the site to enroll subjects into the study at an acceptable rate;
- Failure of the site to comply with pertinent governmental regulations as appropriate;
- Submission of knowingly false information from the research facility to the Sponsor, Clinical Monitor, or governmental authority;
- Failure to adhere to the protocol requirements;
- Data recording is inaccurate or incomplete;
- Investigator does not adhere to the protocol or applicable regulatory guidelines in conducting the study.

#### **10.4.3.** Study Termination Procedures

If the study is terminated by Enanta Pharmaceuticals, Inc. for one of the reasons listed previously, or upon completion of the study, the following activities must be conducted by the Study Monitor and/or site staff:

- Return of all study data to Enanta Pharmaceuticals, Inc. or designee;
- Respond to and complete all requests for data clarifications;
- Accountability and final disposition of used and unused study drug;
- Review of site records for completeness;
- Shipment of all applicable biological samples (including PK samples) to the designated laboratory.

# 11. STATISTICAL CONSIDERATIONS

## 11.1. Sample Size Considerations

## 11.2. General Considerations

Statistical analysis of this study will be the responsibility of Enanta Pharmaceuticals, Inc. or its designee. Details of the statistical analysis methods will be described in the statistical analysis plan (SAP) document. Statistical methods are primarily descriptive in nature and will be used to guide decisions as to the clinical relevance of findings. No formal statistical analysis is planned. Parts 1 and 2 will be summarized separately unless stated otherwise.

Unless otherwise specified, baseline will be defined as the last non-missing measurement before the first dose of study drug. For analyses of nasal swab data and analyses of RSV-related signs and symptoms, if assessments before the first dose of study drug are not available, a post-treatment assessment collected no more than 60 minutes after the first dose of study drug will be used as the baseline value. Any change to the data analysis methods described in the protocol will require an amendment if it changes a principal feature of the protocol. Any other change to the data analysis methods described in the protocol, and the justification for making the change, will be described in the clinical study report or SAP. Changes may only be made in the SAP before unblinding.

The presence of a coinfection will be taken into consideration when analyzing the results of the study.

